8.6.4.1. Adverse Events

The Medical Dictionary for Regulatory Activities (MedDRA, version 20.0) will be used to classify all AEs. Adverse event summaries will include only treatment-emergent AEs (TEAEs). Treatment-emergent adverse events (TEAEs) are defined as AEs that first occurred or worsened during the indicated treatment period.

The number and percentage of patients with TEAEs will be summarized by system organ class (SOC) and preferred term (PT). Summaries of AEs by severity and relationship to the study treatment will also be provided. Serious adverse events (SAEs) and AEs resulting in discontinuation will be summarized separately in a similar manner. Patient listings of AEs and SAEs will be produced.

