7.7.2 Adverse Events

All AEs recorded on the eCRF will be coded using the MedDRA dictionary [Version 21.0 (or a later version if updated during the study)] and classified as treatment – emergent AEs (TEAEs) as follows:

- TEAEs are events with start date on or after the date of first dose of double-blind IMP and up to 14 days after the last dose of double blind IMP or events with start date prior to the date of first dose of double-blind IMP whose severity worsens on or after the date of first dose of double-blind IMP.

All AE data will be listed by treatment group. Treatment-emergence status will be flagged in the listing. In addition, corresponding listings of treatment-emergent serious AEs (TESAEs), AEs leading to permanent discontinuation of IMP and AEs resulting in death will be produced.

Summary tables of TEAEs by treatment group and overall will be produced for the Safety population. No statistical comparisons of AEs between treatment groups will be performed.

The severity of all AEs is recorded as mild, moderate, or severe. If severity is missing for a TEAE, it will be considered severe.

The relationship between an AE and IMP treatment is assessed as definite, probable, possible, unlikely or not related. A treatment-related AE is an AE considered by the investigator as definitely, possibly, or probably related to IMP treatment or with unknown/missing relationship to IMP treatment.

An overview table will summarize the number and percentage of patients with at least one of the following TEAEs, where patients with more than one TEAE in a particular category are counted only once in that category:

- any TEAE;
- TEAE by severity (mild, moderate, severe);
- treatment-related TEAE;
- severe treatment-related TEAE;

COVANCE INC. CONFIDENTIAL

Document Date: 9 July 2018

Page 26 of 39
ST-AD-008 version 04

Downloaded by PPD on 10/12/2022

Statistical Analysis Plan

Sponsor Name: Insys Development Company, Inc.

Sponsor Protocol ID: INS011-16-085

Covance Study ID: 000000163564

- TESAE;
- TESAE by severity;
- treatment-related TESAE;
- TEAE leading to study drug discontinuation.

The overview table will be repeated to summarize the number of TEAEs (displaying the number and percentage of observed events).

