The number and percentage of patients reporting each AE will be summarized by System Organ Class (SOC) and Preferred Term (PT) for the Safety population. Tables will be sorted alphabetically by SOC. PTs will be sorted by descending overall total. The following summaries will be produced:

- AEs occurring in the run-in period, by SOC and PT;
- TEAEs, by SOC and PT;
- TEAEs related to IMP treatment, by SOC and PT;
- TEAEs by relationship to IMP treatment, by SOC and PT;
- TEAEs by maximum severity, by SOC and PT;
- TEAEs related to IMP treatment by maximum severity, by SOC and PT;
- TEAEs causing discontinuation from IMP treatment, by SOC and PT;
- TEAEs related to IMP treatment causing discontinuation from IMP treatment, by SOC and PT;
- TESAEs, by SOC and PT;
- TESAEs related to IMP treatment, by SOC and PT;
- TEAEs leading to death, by SOC and PT.

In the above summaries, patients with more than one TEAE within a particular SOC are counted only once for that SOC. Similarly, patients with more than one TEAE within a particular PT are counted only once for that PT. For summaries by maximum severity, patients with multiple TEAEs within a particular SOC or PT will be counted under the category of their most severe TEAE within that SOC or PT. TEAEs with missing intensity/severity will be included (as severe) in the overall count of patients with TEAEs, but will not be included in the counts of patients with TEAEs within a SOC or PT.

COVANCE INC. CONFIDENTIAL

Document Date: 9 July 2018

Page 27 of 39
ST-AD-008 version 04

Downloaded by PPD on 10/12/2022

Statistical Analysis Plan

Sponsor Name: Insys Development Company, Inc.
Sponsor Protocol ID: INS011-16-085

Covance Study ID: 000000163564

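### SAP 7.7.2 treats a TEAE with missing severity as severe, then leaves it out of the SOC and preferred-term counts

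*SAP*

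**What the plan says.** SAP 7.7.2 sets a general rule for ungraded events: "If severity is missing for a TEAE, it will be considered severe". The rule is not limited to any table.

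After listing the tables by SOC and PT, the same section says: "TEAEs with missing intensity/severity will be included (as severe) in the overall count of patients with TEAEs", and continues: "but will not be included in the counts of patients with TEAEs within a SOC or PT".

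Two sentences bear on which tables this covers. The paragraph opens with all of the listed tables in view: "In the above summaries, patients with more than one TEAE within a particular SOC are counted only once for that SOC". The sentence just before the exclusion is narrower and begins: "For summaries by maximum severity, patients with multiple TEAEs within a particular SOC or PT will be counted under the category of their most severe".

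Other outputs are not touched by the exclusion. On the overview table the section says: "An overview table will summarize the number and percentage of patients with at least one of the following TEAEs". On listings it says: "All AE data will be listed by treatment group". Protocol 8.6.4.1 plans patient counts and percentages for TEAEs at SOC and PT level and makes no exception for ungraded events. SAP 6.2 and Protocol 8.6.6 both rule out imputing missing safety data.

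**The concern.** An event's SOC and PT come from MedDRA coding, which does not need a severity grade. A blank grade says nothing about whether the event happened or what it was, so it gives no reason to drop the event from an incidence row. The SAP's other rules for incomplete adverse event data keep the event in view: an unknown relationship counts as treatment-related (7.7.2), and an onset date too incomplete to place the event counts as treatment-emergent (6.2).

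At stake are the row counts in the SOC and PT tables and their agreement with the overall count. Adverse events are summarised descriptively with no test between groups, so these counts are read at face value. A programmer following the section also has two instructions that cannot both be met.

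**Working it through.** The documents give no figure on this point, so there is nothing to reproduce. The check sets the rules side by side and then sizes one lost patient.

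**1. Scope.** SAP 7.7.2 lists 11 tables by SOC and PT. One covers the run-in period and is not a TEAE table, which leaves 11 − 1 = 10. Two of the ten are by maximum severity (all TEAEs, and related TEAEs), which leaves 10 − 2 = 8 others: all TEAEs, related, by relationship, two for discontinuation, two for serious events, and deaths.

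**2. One ungraded TEAE followed through the outputs** (the patient has no other event in that SOC or PT):

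| Output | General rule | Exclusion read broadly | Exclusion read narrowly |
|---|---|---|---|
| Overall count, overview table | counted, severe | counted, severe | counted, severe |
| SOC and PT rows, 8 other tables where the event qualifies | counted | not counted | counted |
| SOC and PT rows, 2 maximum-severity tables | counted, severe | not counted | not counted |
| Listings | shown | shown | shown |

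The maximum-severity row of the table conflicts with the general rule on both readings. The row for the other eight tables conflicts only on the broad one.

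**3. When a patient is lost.** Rows count patients, not events. A patient disappears from a PT row only if every event of that PT in that patient is ungraded, and likewise for a SOC row. A patient with one mild and one ungraded event of the same term stays in the row, but the maximum severity shown is mild, where the general rule would give severe.

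**4. Size of one lost patient.** SAP 2.3 plans 33 randomised patients per arm. One patient is 1/33 = 3.0 percentage points. As an illustration, 6/33 = 18.2% would be shown as 5/33 = 15.2%.

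**5. Size over a range.** The share m of TEAEs with missing severity is not in the documents; 1% to 10% is assumed. With true PT rate p and one event per patient, the reported rate is p × (1 − m).

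| p | m = 1% | m = 5% | m = 10% |
|---|---|---|---|
| 20% | 19.8% | 19.0% | 18.0% |
| 30% | 29.7% | 28.5% | 27.0% |

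The expected shortfall is p × m: 0.2 to 2.0 points at p = 20%, and 0.3 to 3.0 points at p = 30%. It is zero if no grade is missing, and smaller where patients have further graded events of the same term.

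For a 20% term (0.20 × 33 = 6.6, rounded to 7 patients), the chance that at least one patient is lost is 1 − (1 − m)^7, or 6.8%, 30.2% and 52.2% at m = 1%, 5% and 10%, if missing grades are independent.

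**The case against.** The strongest reply is about scope. The exclusion directly follows the sentence on maximum-severity summaries, and a missing grade matters most in a table classified by grade. On that reading the other eight tables lose nothing. This stands as a plausible reading, but it does not remove the conflict: the maximum-severity tables are exactly where taking a missing grade as severe should apply.

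The second reply is that the situation may hardly arise. SAP 7.7.2 says severity is recorded for all adverse events, Protocol 6.2.6.2 and 6.2.6.7 require the investigator to grade them, and Protocol 10.3 and 12.1 provide for data review before lock and for queries. This stands, and it keeps the expected effect small.

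The third is that nothing is lost to the record, since the overview tables and listings hold every event. This also stands. It limits the harm but does not correct the rows.

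The fourth is that counting missing as severe is itself an imputation, which SAP 6.2 and Protocol 8.6.6 rule out, and that a separate row for missing, the display default in SAP 7.1, would serve as well. That is a defensible alternative. However, 7.7.2 has already chosen to treat missing as severe, so the shorter route is to apply that choice throughout and state the exception.

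A reader might go further and infer that the trial's main safety tables under-report adverse events in general, or that the comparison of arms is distorted. The documents support neither. The broad scope is not certain, no frequency of missing grades is given, TEAEs are not ranked above the other safety endpoints, no test on adverse events is planned, and nothing suggests that grades would be missing more often in one blinded arm.

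**Conclusion.** The contradiction within SAP 7.7.2 is real and holds on either reading of its scope. Followed as written, the exclusion gives wrong SOC and PT counts in at least the two maximum-severity tables and at most all ten TEAE tables. Where it changes a patient count, it can only lower it.

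The effect is probably small: 3.0 percentage points for each patient lost at 33 per arm, and none if every TEAE is graded. The range in the working rests on an assumed 1% to 10% of ungraded events and one event per patient. The 33 is the number randomised per arm; a patient weighs more in the separate 30 and 40 mg/kg/day columns, whose sizes are not known in advance. The point is worth correcting because the text gives two incompatible instructions and the correction is nearly free, not because a large bias is expected.

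**What to change.** In SAP 7.7.2:

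- Delete the clause that excludes ungraded TEAEs from the SOC and PT counts.
- State that every coded TEAE counts in its SOC and PT in every table where it qualifies, whatever its severity status.
- State that in the two maximum-severity tables a missing grade counts as severe, in line with the general rule, with a footnote giving the number of ungraded events.

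In SAP 6.2, name this as an exception to the no-imputation statement. Because Protocol 8.6.6 says the same, note the exception in SAP section 8 as well, which now reads as not applicable.

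The cost is a few sentences before programming, with no new data and no effect on the efficacy analyses. The one downside is that severe counts for individual terms may be slightly higher than the investigators' grades alone would give; the footnote lets a reader see by how much.

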7.7.3 Laboratory Evaluations

7.7.3.1 Standard Safety Laboratory Panel

Data for the following hematology, blood chemistry, and urinalysis analytes received from central laboratory will be listed and summarized by treatment group and visit. If data for any additional analytes are also received or recorded, then these will be listed only.

Hematology	Serum Chemistry	Urinalysis
Hemoglobin	Albumin	pH
Hematocrit	Blood Urea Nitrogen	Specific Gravity
Total Leukocyte Count	Creatinine	Protein
Differential Leukocyte Count	Total Bilirubin	Glucose
Red Blood Cell Count	Alkaline Phosphatase (ALP)	Ketones
Platelets	Aspartate Transaminase (AST)	Bilirubin
Neutrophils (abs, %)	Alanine Transaminase (ALT)	Blood
Lymphocytes (abs, %)	Sodium	Nitrite
Monocytes (abs, %)	Potassium	Leukocyte Esterase
Eosinophils (abs, %)	Chloride	Urobilinogen
Basophils (abs, %)	Lactate Dehydrogenase (LDH)	Color and Clarity
White Blood Count	Uric Acid	Microscopic
	Glucose	Urine T. Protein, Random
	Calcium	Urine Creatinine, Random

All laboratory data will be reported in Conventional units. Out-of-reference-range values will be flagged as high (H) or low (L) in the listings.

For analysis purposes, values preceded by a "<" or a ">" sign (i.e. those below or above the limits of quantification) will be considered equal to the lower or upper limit of quantification, respectively.

Laboratory and urinalysis data will be summarized by visit using standard descriptive statistics for the Safety population. Changes from baseline will also be summarized.

Statistical Analysis Plan

Sponsor Name: Insys Development Company, Inc.

Sponsor Protocol ID: INS011-16-085

Covance Study ID: 000000163564

For hematology and serum chemistry, shift tables presenting movement in and out of reference ranges from baseline to each scheduled post-baseline visit will be provided for each treatment group. Corresponding shift tables will be produced for urinalysis.

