- Safety Population: The Safety Population will include all patients who were treated with at least one dose of the study drug.
- Intent to Treat (ITT) Population: The ITT Population will include all patients who were randomized.

Efficacy Analyses

The ITT Population will be used for all efficacy analyses.

The primary efficacy endpoint will be tested using a 2-sided type I error rate of 0.05. The primary outcome variable for the study is the change in total score of the HQ-CT from Baseline through Study Completion/Early Withdrawal.

Statistical inference for the primary endpoint and for the secondary endpoints (change in total body-weight, responder rate, PGI-C and PGI-S, TFEQ-R18, and PROMIS Life Satisfaction and Positive Affect, PROMIS Physical Activity and Fatigue), will be controlled at an overall family wise error rate (alpha) of 0.05, 2-sided.

For continuous endpoints, number of observations, mean, standard deviation (SD), median, minimum, and maximum, will be presented as descriptive statistics. For inferential statistics, analysis of covariance (ANCOVA) with the baseline value and randomization strata (growth hormone treatment) as covariates.

For categorical endpoints, the number of observations, frequency counts and percentages will be presented as descriptive statistics. Fisher's exact test will be used for inferential statistics.

Safety Analyses

The Safety Population will be used for all safety assessments.

All safety assessments will be descriptive and no inferential statistics are planned. All data listings will be provided for protocol specified safety data. The Medical Dictionary for Regulatory Activities (MedDRA; Version 20.0 or higher) will be used to classify all adverse events with respect to system organ class and preferred term. Adverse event summaries will include only TEAEs by treatment group. All clinical laboratory findings and vital signs will be summarized for all patients in the safety population for observed values and change from

baseline. Shifts from baseline according to normal range criteria will also be presented for all patients in the safety population. Prior medication and concomitant medications will be reported in the data listings.

Statistical analyses will be performed using SAS[®] (Version 9.3 or higher, SAS Institute Inc.).

Pharmacokinetic Analyses

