3.2. Patient Selection

3.2.1. Inclusion Criteria

All patients must satisfy the following criteria to be considered for study participation:

1. Patient and/or parent(s)/caregiver(s) fully comprehend the informed consent form (ICF) and assent form, understand all study procedures, and can communicate satisfactorily with the investigator and study coordinator, in accordance with applicable laws, regulations, and local requirements.
2. Males and females from 8-17 years of age, inclusive.
3. Genetically confirmed diagnosis of Prader-Willi Syndrome using standard DNA methylation test or fluorescent *in situ* hybridization. Documentation of genetically confirmed diagnosis of Prader-Willi Syndrome is acceptable.
4. A score of ≥ 10 on the HQ-CT.
5. A caregiver is available to complete the HQ-CT.
6. If female, is either not of childbearing potential (defined as premenarchal or surgically sterile [bilateral tubal ligation, bilateral oophorectomy, or hysterectomy]) or practicing one of the following medically acceptable methods of birth control:
 - a. Hormonal methods such as oral, implantable, injectable, vaginal ring, or transdermal contraceptives for a minimum of 1 full cycle (based on the patient's usual menstrual cycle period) before study drug administration.
 - b. Total abstinence from sexual intercourse since the last menses before study drug administration.
 - c. Intrauterine device.
 - d. Double-barrier method (condoms, sponge, or diaphragm with spermicidal jellies or cream).
7. Adequate renal function, defined as serum creatinine $\leq 1.5 \times$ upper limit of normal (ULN) and urine protein/creatinine ratio < 0.2 .
8. Adequate hepatic function, defined as total bilirubin $\leq 1.5 \times$ ULN and aspartate aminotransferase (AST) and Alanine aminotransferase (ALT) levels $\leq 3 \times$ ULN.
9. Growth hormone treatment will be permitted if doses have been stable for at least 1 month prior to screening.
10. Psychotropic treatment will be permitted and should be stable at least 6 weeks prior to screening.
11. Any other treatment including thyroid hormones should be stable for at least 6 weeks prior to screening.

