3.6. Stopping Rules

The Investigator reserves the right to terminate the study in the interest of patient safety and welfare. The Sponsor reserves the right to terminate the study at any time for administrative reasons. Patients will also be discontinued when their liver enzymes and serum bilirubin reach:

- ALT or AST > 8 x ULN
- ALT or AST > 5 x ULN for more than 2 weeks
- ALT or AST > 3 x ULN and (TU>2 x ULN or INR>1.5)
- ALT or AST > 3 x ULN with appearance of fatigue, nausea, vomiting, right upper quadrant pain or tenderness, fever, rash, and/or eosinophilia (> 5%)

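### The planned chemistry shift table grades ALT, AST and bilirubin only as low, normal or high, so no output counts patients per arm by multiple of ULN, the scale on which the protocol sets its liver criteria

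*SAP*

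**What the plan says.** SAP 7.7.3.1 lists ALT, AST and total bilirubin in the serum chemistry panel. Its only categorical output for that panel is the shift table, given by treatment group: "For hematology and serum chemistry, shift tables presenting movement in and out of reference ranges from baseline to each scheduled post-baseline visit". The only grading mentioned anywhere is in the listings: "Out-of-reference-range values will be flagged as high (H) or low (L) in the listings". The Safety Analyses paragraph of the protocol synopsis uses the same scheme: "Shifts from baseline according to normal range criteria will also be presented for all patients in the safety population".

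The section also plans descriptive statistics by visit for values and for change from baseline, in conventional units. SAP 7.1 restricts tables to scheduled post-baseline visits and leaves everything else to the listings. The schedule of assessments has chemistry only at Screening and at Visit 10/Early Withdrawal; the Week 3 sample is a blood count.

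Two parts of the protocol work on a different scale. Inclusion criterion 8 (Protocol 3.2.1), which begins "Adequate hepatic function, defined as total bilirubin", sets the entry limit at 1.5 x ULN for bilirubin and 3 x ULN for ALT and AST. Protocol 3.6 then lists four liver criteria for discontinuing a patient. The first is "ALT or AST > 8 x ULN". The others are >5 x ULN lasting beyond two weeks, >3 x ULN with either a TU or an INR elevation, and >3 x ULN with symptoms or eosinophilia.

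**The concern.** A patient may enter with ALT or AST already above the reference range. For that patient the table has no higher category, so no rise of any size can appear as a shift. For a patient who enters within range, every rise past the upper limit goes to the same cell, whether it is measurement noise or a several-fold increase.

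Safety and tolerability is a secondary objective, and liver tests are the only laboratory measures for which Protocol 3.6 sets numeric discontinuation criteria. A reader of the study report will want to know how many patients in each arm passed 3, 5 and 8 x ULN. As written, the SAP does not produce that number.

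**Working it through.** The plan gives no figure to reproduce here, so the check is to apply the stated rule to examples and then ask what the other outputs add.

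**Rule.** Taking the top of the reference range as 1 x ULN, a value is High if it exceeds 1 x ULN. A shift is visible only if the category changes between baseline and the post-baseline visit. For comparison, the same pairs are placed in bands cut at 1 and at the 3, 5 and 8 x ULN points of Protocol 3.6.

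| Baseline to post-baseline (x ULN) | Change | SAP table | Bands in x ULN |
|---|---|---|---|
| 2.5 to 8.5 | 8.5/2.5 = 3.4-fold, +6.0 | High to High, no shift | >1-3 to >8 |
| 2.5 to 2.6 | 2.6/2.5 = 1.04-fold, +0.1 | High to High, no shift | >1-3, unchanged |
| 0.95 to 8.5 | 8.5/0.95 = 8.95-fold, +7.55 | Normal to High | <=1 to >8 |
| 0.95 to 1.05 | 1.05/0.95 = 1.11-fold, +0.10 | Normal to High | <=1 to >1-3 |

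The first two rows are indistinguishable in the SAP table, and so are the last two. The bands separate both pairs. This result needs no assumption about how ALT is distributed.

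**What the other planned outputs add.**
- Descriptive statistics (SAP 7.7.3.1): an extreme value can appear as a maximum or maximum change, in conventional units, with no count of patients.
- TEAE tables (SAP 7.7.2): these count patients by preferred term, severity and discontinuation. Under Protocol 6.2.6.1, however, a laboratory value becomes an adverse event through the investigator's judgement of its importance.
- Disposition (SAP 7.2): this counts early discontinuations by primary reason, not by liver value.
- Listings: every value is there, but nothing is counted.

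None of these gives patients per arm by multiple of ULN.

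**How much is hidden.** The documents give no ALT distribution, so this can only be shown as a range under assumptions. Let a patient's underlying ALT (x ULN) be log-normal with median 0.5 or 0.7. Each reading varies with CV 20% or 30%, baseline is capped at 3, and a random 10% of patients have a k-fold rise. The quantity is the share of post-baseline values above 5 x ULN whose baseline was already above 1, that is P(baseline >1 and post >5) / P(post >5). Ranges are over the median and CV settings, by simulation.

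| Between-patient log SD | 6-fold | 10-fold | 15-fold |
|---|---|---|---|
| 0.45 | 37-56% | 16-33% | 10-27% |
| 0.30 | 18-39% | 5-24% | 3-21% |

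The fold rise drives the result because passing 5 x ULN needs an underlying level of about 5/k: 0.83 for 6-fold, 0.50 for 10-fold, 0.33 for 15-fold. The smaller the rise, the more the cases above 5 come from patients who started high.

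**The case against.** The strongest reply is that nothing is lost. Each patient has about two scheduled chemistry results, all values are listed and flagged, and with about 66 patients a reader could count by hand. A patient who meets a Protocol 3.6 criterion is to be discontinued, so the case should also reach the disposition table and, if recorded as an adverse event, the TEAE and discontinuation tables by arm. The SAP follows the protocol synopsis, so there is no contradiction, and table shells we have not seen may hold more detail.

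Much of this stands. It limits the point to a gap in tabulation. It does not close the gap: the adverse event route depends on investigator recording, the disposition table records a reason and not a level, and a hand count is not a planned output.

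Three stronger readings are tempting and not supported.
- A reader might infer that a patient passing a discontinuation threshold would go unnoticed. Protocol 3.6 acts on the individual patient's values, not on this table.
- A reader might infer that noise in the Normal to High cell weakens a between-arm comparison. Protocol 8.6.4 plans no inferential safety analysis, so no test is affected.
- A reader might infer that about half of all large rises would be hidden. That holds only near the top of the range above and rests on inputs the documents do not give.

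A banded table confined to scheduled visits would also fall short. SAP 7.1 leaves one post-baseline chemistry value per patient, so a peak found at an unscheduled draw would be missed.

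**Conclusion.** The point holds as a reporting gap. The generic chemistry shift table cannot show any rise from an ALT/AST baseline above 1 and up to 3 x ULN, and it merges small with large rises from a normal baseline. No other planned output counts patients per arm against the numeric cut-points of Protocol 3.6. This follows from the text alone.

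The number of patients affected does not. Under the assumed log-normal ALT, the hidden share of cases above 5 x ULN runs from about 3% to 56%, depending mainly on the spread and the fold rise. The efficacy analyses and the protocol's liver criteria themselves are not touched. The change is worth making because it is cheap and liver tests are where the protocol itself sets limits.

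**What to change.** In SAP 7.7.3.1, keep the reference-range shift tables and add one table by treatment arm for ALT, AST and total bilirubin, crossing baseline band with maximum post-baseline band in multiples of ULN:
- ALT and AST: <=1, >1-3, >3-5, >5-8, >8.
- Total bilirubin: <=1, >1-1.5, >1.5-2, >2.

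Include unscheduled and early-withdrawal values, and state this as an exception to the scheduled-visits-only rule in SAP 7.1.

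Add a count per arm of patients with ALT or AST >3 x ULN together with bilirubin >2 x ULN. First ask the sponsor to confirm that TU in Protocol 3.6 means total bilirubin. The lead-in to that list mentions serum bilirubin, which suggests so, but the abbreviation is not defined.

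State in the SAP that the table reports numeric cut-points only. It cannot count the duration, INR or symptom parts of Protocol 3.6, and INR is not in the planned panel.

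The cost is one more programmed table, with small cell counts. It needs no new samples, and the upper limits are already required for the planned high/low flags.
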